2.3.3 Efficacy Data in Adults with Cancer

Pazopanib 800 mg once daily has shown efficacy and/or encouraging efficacy signals in the following settings:

• RCC: The primary analysis of the primary endpoint, progression-free survival (PFS), revealed a large and highly statistically significant improvement in PFS in the pazopanib-treated patients compared to placebo- treated patients (hazard ratio [HR] 0.46, 95% confidence interval [CI] 0.34 to 0.62, p<0.0000001). The median PFS in the pazopanib arm was more than double that in the placebo arm: 9.2 months (95% CI, 7.4, 12.9) versus 4.2 months (95% CI, 2.8, 4.2), respectively. The response rate (RR), defined as the percentage of patients who achieved either a confirmed complete response (CR) or partial response (PR)

according to Response Evaluation Criteria in Solid Tumors (RECIST) was significantly higher for the pazopanib arm compared with the placebo arm by Independent Review Committee (IRC) assessment (30% vs. 3%, p<0.001). In the pazopanib arm, the median duration of response was 58.7 weeks (95% CI, 52.1 to 68.1 weeks) and the median time to response was 11.9 weeks (95% CI, 9.4 to 12.3 weeks) by IRC assessment.²⁹ The median OS at final analysis was 22.9 months in the pazopanib arm and 20.5 months in the placebo arm. The final OS was not statistically different between the pazopanib arm and the placebo arm in (HR = 0.91, stratified log-rank p-value, 0.224). Of note, 54% of patients in the placebo arm received pazopanib, many starting early in the study, and an additional 12% received other systemic therapies.

- Soft Tissue Sarcoma: In a Phase III study a statistically significant improvement in PFS but not OS was observed in the pazopanib arm compared with the placebo arm. Median progression-free survival was 4.6 months for pazopanib compared with 1.6 months for placebo (hazard ratio [HR] 0.31, 95% CI 0.24-0.40; p<0.0001). Overall survival was 12.5 months with pazopanib versus 10.7 months with placebo (HR 0.86, 0.67-1.11; p=0.25).³⁰ In a Phase II Study, the PFS rate at 12 weeks, based on investigator assessment, was 18 of 41 patients (43.9%) for leiomyosarcoma;18 of 37 patients (48.6%) for synovial sarcoma; 5 of 19 (26.3%) for adipocytic sarcoma; and 16 of 41 patients (39.0%) for other types of sarcoma.³¹
- Ovarian cancer: 11 of 36 patients (31%) experienced a cancer antigen-125 (CA-125) response to pazopanib, with a median time to CA-125 response of 29 days and median duration of response of 113 days. Excluding one patient whose CA-125 decreased before she received the first dose, the biochemical response was 28% (10 patients). Overall response rate based on modified Gynecologic Cancer Intergroup (GCIG) criteria (incorporating CA-125, RECIST, and clinical assessment) was 18% in patients with measurable disease at baseline, and was 21% in patients without measurable disease at baseline. Median PFS was 84 days.³²
- Early-stage Non-Small Cell Lung Cancer (NSCLC): 30 of 35 patients (86%) experienced a reduction in tumor volume after short-term use of pazopanib (median duration of 16 days) as assessed by high-resolution computed tomography (HRCT) after preoperative pazopanib treatment.³³
- ErbB2-positive advanced or metastatic breast cancer: A higher response rate (36.2% versus 22.2%) by independent review at Week 12 was observed in patients on combination lapatinib 1000 mg once daily + pazopanib 400 mg once daily compared with lapatinib 1500 mg once daily as a monotherapy, respectively.³⁴
- **Cervical cancer:** There was a 34% reduction in risk for progression for patients receiving pazopanib relative to lapatinib (hazard ratio: 0.66; 90% CI: 0.48, 0.91). The median time to investigator-assessed PFS was 17.1 weeks in the lapatinib group and 18.1 weeks in the pazopanib (one-sided p=0.013).³⁵

Pazopanib has not shown signals of efficacy in Phase II studies conducted in multiple myeloma (VEG20006)³⁶ or glioma (VEG102857).

Most important to the rationale for this current trial are the results from the study of pazopanib in adult patients with advanced or metastatic soft tissue sarcoma. These combined findings form the basis for including several cohorts for soft tissue and bone sarcoma as well as the embryonal tumors specific to pediatrics, which are of mesenchymal origin. To date, results of correlative biologic assays specific to pazopanib are limited. Most studies sample platelet-poor plasma and serum for cytokine/angiogenic factor profiling which include VEGF, sVEGFR1, and sVEGFR2 and whole blood for circulating endothelial cell subsets (CECs). In two separate Phase II studies of renal cell and NSCLC presented at the 2008 annual meeting of the American Society for Clinical Oncology (ASCO) a decrease in sVEGFR2 compared with baseline was significantly correlated with tumor response (p < 0.05).^{37,38} In adult patients with metastatic imatinib-refractory gastrointestinal stromal tumors treated with sunitinib, another VEGF and c-kit targeting multityrosine kinase inhibitor, biomarker analysis of CECs, monocytes, VEGF, and sVEGFR-2 were consistently modulated by treatment. In this study, changes in CECs and monocytes rather than plasma markers differed between the patients with clinical benefit and those with progressive disease.³⁹ In pediatric patients with refractory solid tumors treated with pazopanib, baseline levels of plasma soluble VEGFR-2 and endoglin levels were significantly decreased when measured after 2 weeks of treatment, while placental growth factor levels were significantly increased over the same time points. There was no significant change in VEGF or plasma soluble VEGFR-1 levels with pazopanib therapy.⁴⁰

This study will continue to examine the effects of pazopanib therapy on cytokines and angiogenic factors.

In part, genetic predisposition may account for the variability in biomarker or clinical response to anti-VEGF treatment. Three lines of ongoing investigation justify voluntary collection of DNA in this trial to evaluate relationships between discovered associations in the adult population and pazopanib effects in the pediatric population, and to assess age as a covariate in these relationships.

- colleagues identified a single nucleotide 1) Recently, Dr. and polymorphism in KDR (the gene that encodes VEGFR2) that is reproducibly associated with the baseline levels of circulating soluble VEGFR2 in three separate cohorts: healthy volunteers of the Old Order Amish community; 128 unrelated cancer patients at the ; and adult RCC patients enrolled on the phase II trials of pazopanib. Subsequently, they demonstrated that in the RCC patients treated with pazopanib for 4 weeks, this polymorphism is associated with a greater magnitude decline in plasma sVEGFR2 (Late Breaking Abstract, 2011 Am Soc Clin Pharm & Therapeutics Meeting). This genotype/phenotype relationship is currently being studied by another cooperative group (the CALGB Pharmacology and Experimental Therapeutics Committee) in adult patients who are taking agents in this class. Determination of the effect of this KDR polymorphism and sVEGFR2 degree of change on disease response to therapy is ongoing.
- 2) Several genotypes at the VEGFA locus have been associated with increased or decreased VEGF production and prognostic and predictive marking of treatment outcomes. In most VEGF signaling pathway inhibitor trials analyzed so far, 4 SNPs in the promoter region have been evaluated for associations with clinical outcomes: -2578, -1498, -1154, and -634. These studies have yielded inconsistent findings. In amyotrophic lateral sclerosis, similar inconsistencies led to confusion on the predictive role of VEGF alleles until a meta-analysis by Lambrechts, et al.⁴¹ revealed only -2578 to have a clinically relevant and consistent effect. Such studies in oncology are ongoing.

We propose to evaluate all common variation across the VEGFA locus with tagging SNPs representing all common variation in the haplotype analyzed for association with changes in VEGF-A post pazopanib exposure, response rate, and progression-free survival.

3) GlaxoSmithKline has recently published results of a candidate gene association study in adult RCC patients treated with pazopanib.²⁵ Several polymorphisms in candidate genes demonstrated associations with response rate and progression-free survival. Validation and elaboration of these findings will become available prior to completion of this trial. Based on the adult findings, additional markers may be explored in the pediatric population.

2.4 Pediatric Studies

2.4.1 Pediatric Phase I Studies

The Children's Oncology Group (COG) conducted a phase I study of pazopanib in children with STS or other refractory solid tumors (ADVL0815). This study was performed to determine the maximum tolerated dose (MTD) of two formulations of oral pazopanib; to define and describe the toxicities, pharmacodyamics and pharmacokinetics (PK) of pazopanib administered as a tablet (Part 1) or powder suspension (Part 2a); and to explore pazopanib induced changes in tumor blood volume and vascular permeability (Ki) using dynamic contrast enhanced MRI (DCE-MRI) in a subset of patients with STS (Part 2b). During part 1, pazopanib (tablet formulation) was administered once daily in 28 day cycles at 4 dose levels (275 to 600 mg/m²) using the rolling-six design. Dose determination for a powder suspension (Part 2a) was initiated at 50% of the MTD for the intact tablet. Ten patients with STS underwent DCE-MRI scanning at baseline and 15 ± 2 days after initiation of pazopanib at the tablet MTD (Part 2b). A total of 53 patients were enrolled; 51 were eligible [26 male, median age 12.9 yrs (range 3.8-23.9)].

Hematologic and non-hematologic toxicities were generally mild. Diarrhea, nausea, vomiting, fatigue, proteinuria and hypertension were the most commonly reported side effects. Only cycle 1 DLTs were considered for determination of the MTD and included Grade 3 lipase, amylase and ALT elevation, proteinuria and hypertension. One patient with occult brain metastasis in the imaging expansion cohort also had Grade 4 intracranial hemorrhage. The MTD was 450 mg/m²/dose for tablets, and 160 mg/m²/dose for powder suspension; two isolated and reversible Grade 3 ALT elevations were seen at the powder suspension dose of 225 mg/ m²/dose. Toxicities requiring dose modification and/or discontinuation in later cycles included tumor pain (n=2), ALT elevation (n=2), diarrhea, myalgia associated with microangiopathic hemolytic anemia, hand foot syndrome, weight loss, fistula formation at a site of prior RT, growth plate abnormality and recurrent neutropenia (each n=1). Three of 27 patients treated at the MTD had asymptomatic decreases in left ventricular systolic function; all were reversible and the drug was successfully reintroduced in two. Asymptomatic sinus bradycardia was noted in 4 patients, all ≥ 12 years. No QTc prolongation was observed.

Steady state trough concentration (Ctrough) was reached by day 15 and exceeded 15μ g/ml at all dose levels. There was marked inter-patient variability in PK parameters resulting in substantial overlap between dose levels and trough concentrations did not appear dose-dependent. Patients received $1-22^+$ cycles

(median = 2). One patient each with hepatoblastoma or desmoplastic small round and all 5 who received therapy for a year or more had Ctrough $\ge 30 \,\mu\text{g/ml}$. All patients with evaluable DCE-MRI (n=8) experienced decreases in tumor blood volume and permeability (Ki; p<0.01). PIGF increased, whereas endoglin and soluble VEGFR2 decreased (p<0.01; n=31).⁴⁰

2.4.2 Pharmacology/Pharmacokinetics/Correlative Biological Studies

Hypertension was seen in several patients in the pediatric Phase I dose escalation study, which is a class effect seen with other VEGF blocking agents. Such hypertension has been treatable with anti-hypertensives and may ultimately be a biomarker of treatment effect. Pediatric specific guidelines for the management of VEGF blocking agent-induced hypertension have been developed for other COG Developmental Therapeutics studies (e.g. ADVL0413, ADVL0612, ADVL0714, and ADVL0815) and will be used for this trial. In the adult Phase I pazopanib trial, a relationship between steady-state trough concentrations and the occurrence of hypertension could be described by a logistic regression model. Twenty (77%) of the 26 patients with Ctrough values > 15 μ g/mL on Day 22 developed hypertension, versus 11 (39%) of the 28 patients who had lower Ctrough values.⁴² In the pediatric phase I trial, the mean Ctrough in patients with drug related hypertension (n=13) was 42±13 g/ml versus 29±13 g/ml in normotensive patients (n=27; p=0.008), suggesting a relationship between blood pressure elevation and drug exposure. In addition pediatric patients with a best response of stable disease had a 30% incidence of blood pressure elevation within the first two cycles, and 47% incidence over all cycles. This trial will seek to expand our understanding of the relationship of pazopanib Ctrough to hypertension, and the utility of hypertension as a pharmacodynamic or predictive marker.

2.5 Overview of Proposed Pediatric Phase II Trial

This is a two-stage open label phase II trial of pazopanib in children, adolescents and young adults with recurrent or refractory solid tumors. Tumors of primary interest are rhabdomyosarcoma, non-rhabdomyosarcomatous soft tissue sarcoma (including synovial sarcoma, alveolar soft part sarcoma and desmoplastic small round cell tumor) and Ewing sarcoma/peripheral PNET. Tumors of secondary interest include hepatoblastoma, neuroblastoma (measurable and evaluable), and osteosarcoma.

Each tumor type defines a cohort resulting in 7 total cohorts. The first stage of the study involves enrolling an initial 10 patients into each cohort. The response rate will be determined for each cohort after the target enrollment of 10 patients is reached for that cohort. If one or more confirmed responses are observed in the first 10 evaluable patients in a cohort, an additional 10 patients will be enrolled into that cohort in the second stage of study. Thus, for cohort(s) with one or more confirmed responses in the first stage of study, a total of 20 patients will be enrolled and evaluated to determine efficacy.

Eligible patients will receive pazopanib monotherapy. Pazopanib will be dosed daily as an oral tablet (450 mg/m²/dose, maximum 800 mg) or as a powder for oral suspension (225 mg/m²/dose, maximum 400 mg) in 28 day cycles.

The MTD for pazopanib tablets was 450 mg/m²/dose as determined by ADVL0815/PZP114411, the COG Phase I study in children with relapsed or refractory solid tumors. For the powder suspension formulation, the selected starting dose is higher than the protocol-defined MTD of 160 mg/m²/dose established in ADVL0815. This decision is driven by the considerations that the 160

isolated and reversible laboratory-defined DLTs were observed at the 225 mg/m²/dose.

The first patients who are enrolled to receive pazopanib as powder suspension at 225 mg/m²/dose daily will be closely monitored for safety and for the occurrence of dose-limiting toxicity during the first cycle (28 days) of therapy. Patients who either receive 225 mg/m²/dose daily for at least 24 days (85% of the dose for a 28-day cycle with powder suspension at 225 mg/m²/dose) or are withdrawn from dosing due to one or more protocol-defined dose-limiting toxicities (Section 5.1) during the first cycle will be considered evaluable for the purpose of this safety review. Six evaluable patients are required.

The first patients enrolled to receive powder suspension at 225 mg/m²/dose will also be expected to complete extended PK sampling (Section 7.3.2) with blood samples collected prior to dosing, and 30 min, 1, 2, 4, 6, and 8 hours after the pazopanib dose on Day 1 and Day 15 \pm 1 day of Cycle 1 (with no pazopanib dose modification or adjustment in the 10 days before Cycle 1 Day 15 sample collection). Patients who can provide adequate blood samples for the 2 scheduled extended PK collections will be considered to be evaluable patients for the purpose of this PK analysis, and PK data are required from 6 evaluable patients. If one or more of the first 6 patients fails to provide blood samples as specified in the protocol or if it is known that for some reason a patient's collected blood sample(s) cannot be analyzed, that patient will be determined to be non-evaluable for this analysis, and one or more additional patients will be enrolled for treatment with pazopanib as powder suspension for the purpose of obtaining the extended PK samples.

Because patients receiving the powder suspension enrolled in the safety review group may be different from those in the PK analysis group, enrollment onto powder suspension may follow several different paths:

- If ≥ 2 out of 6 evaluable patients have dose- limiting toxicities (DLT and as defined in Section 5.1) within the first cycle, then enrollment onto 225 mg/m²/dose pazopanib will be halted. Subsequent new patients will be enrolled at the 160 mg/m²/dose level until 6 evaluable patients from this dose group are available for the safety review and 6 patients are available for PK analysis at 160 mg/m²/dose.
- If 6 PK evaluable patients are enrolled prior to enrollment of 6 patients who are evaluable for the safety review, the extended PK sample collection may be suspended.
- If < 2 DLTs are observed during the first cycle in 6 patients evaluable for safety at 225 mg/m²/dose and these 6 patients are not all evaluable for the PK analysis, then enrollment will continue until 6 PK evaluable patients are available.

All patients will be closely monitored with clinical and laboratory observations for adverse events.

Tumor response will be evaluated using appropriate imaging assessments at baseline, prior to Cycle 3, Cycle 5, Cycle 8, Cycle 11 and then every 3rd cycle thereafter.

In addition, we will assess KDR polymorphism and

pazopanib-induced change in soluble VEGFR2; VEGF-A genotype and changes in VEGF-A concentration; KDR and VEGF-A genotypes and response rate, and progression-free survival; and candidate SNPs and clinical endpoints as identified in the adult population.

The primary analysis will be performed 20 weeks after the last patient's first visit in the three cohorts of primary interest (rhabdomyosarcoma, non-rhabdomyosarcomatous soft tissue sarcoma and Ewing sarcoma/peripheral PNET).

The study will be completed one year from the date of the last patient's first visit and the end of study analysis will be performed at the time of study completion.

For patients who are still on treatment and continue to derive benefit from it at the time of study completion, and for whom no other treatment options are available, Novartis will discuss individual patient cases with investigators to identify possible access to study treatment after termination of the VEG116731/ADVL1322/PZP034X2203 trial.

A patient will be considered to have completed the study if the patient:

- Dies while on study and prior to study completion
- Stays on study in follow-up until the time of study completion

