4.1 Overview of Treatment Plan

Pazopanib will be dosed daily as an oral tablet at 450 mg/m²/dose or as a powder for oral suspension at 225 mg/m²/dose.

For the tablet formulation, the maximum tolerated dose (MTD) was 450 mg/m²/dose as determined by ADVL0815/PZP114411, the COG Phase I study. The maximum dose to be administered daily for tablets is 800 mg.

For the powder suspension formulation, the selected starting dose is 225 mg/m²/dose, higher than the protocol-specified MTD of 160 mg/m²/dose established in study ADVL0815. This decision is driven by the considerations that the 160 mg/m²/dose may result in exposure that is suboptimal to demonstrate efficacy and that only two isolated and reversible laboratory- defined dose-limiting toxicities (DLTs) were observed at the 225 mg/m²/dose. The maximum dose to be administered daily for oral suspension is 400 mg.

Note: The first patients enrolled who receive powder suspension will be reviewed for safety and will be expected to complete extended PK sampling (Section 7.3.2). A minimum of 6 evaluable patients for safety and 6 evaluable patients for PK are required as described in section 2.5. Safety and PK data from these patients will be reviewed prior to further enrollment of patients requiring powder suspension to determine if the 225 mg/m²/dose is tolerated and if the PK exposure is similar to exposure in adults associated with clinical efficacy. If 225 mg/m²/dose is not tolerated (\geq 2 patients with DLTs in the first 6 evaluable patients during their first cycle), all subsequently enrolled patients will receive 160 mg/m²/dose, and an additional 6 subjects will be assessed for safety and PK.

Patients will take pazopanib continuously, once daily. A cycle will be defined as 28 days with no rest periods between cycles. Patients with benefit (stable disease or an objective response) may continue therapy unless there is evidence of progressive disease or unacceptable treatment-related toxicity, death or until study closure defined as 1 year after Last Patient First Visit.

Patients must remain on the same formulation of pazopanib throughout the duration of their protocol therapy.

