5.1 Definition of Dose Limiting Toxicity (DLT)

DLT will be defined as any of the following events that are at least possibly, probably, or definitely attributable to pazopanib. See Section 5.4 for the Potential Pazopanib Specific Side Effects. Dose-limiting hematological and non-hematological toxicities are defined differently.

5.1.1 Hematological Dose-Limiting Toxicity

- a) For patients who are evaluable for hematologic toxicity assessment (patients **without** bone marrow involvement)
 - Grade 4 Thrombocytopenia (platelet count < 25,000/mm3) or Grade 4 neutropenia
 - Any hematologic toxicity requiring dose reduction or treatment interruption for >14 days

b) For all patients:

- \geq Grade 2 arterial thromboembolic events (visceral arterial ischemia, peripheral ischemia, or ischemia cerebrovascular)
- Grade 3 or 4 venous thromboembolic event
- Any thrombotic event (other than central venous line [CVL] associated thrombosis) requiring systemic anticoagulation

5.1.2 Non-Hematological Dose-Limiting Toxicity

- 5.1.2.1 Any Grade 4 non-hematologic toxicity
- 5.1.2.2 Any Grade 3 non-hematological toxicity, with the specific exclusion of the following:
 - Grade 3 nausea and vomiting of less < 3 days duration
 - Grade 3 fever or infection,
 - Grade 3 hypophosphatemia, hypokalemia, hypocalcemia or hypomagnesemia responsive to oral supplementation within 7 days of start of supplement (see Section 5.4.4 for dose modifications)
- 5.1.2.3 Grade 2 allergic reactions that necessitate discontinuation of protocol therapy will not be considered a dose-limiting toxicity.
- 5.1.2.4 Any Grade 2 non-hematological toxicity that persists for \geq 7 days and is considered sufficiently medically significant or sufficiently intolerable by patients that it requires treatment interruption may also be considered a DLT following discussion with the Study chair and a Novartis Medical Lead.
- 5.1.2.5 Hypertension will be graded according to the NCI CTCAE; however, dose limiting hypertension will be considered as the following:

- Grade 4 hypertension
- A blood pressure >25 mmHg above the 95th percentile for age, height, and gender (see Appendix V) confirmed by repeated measurement on the same day (See Sections 5.4.1 and 4.1.5.1 for management)

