5.2 Dose Modifications for Hematologic Toxicity

All dose modifications should be based on the worst preceding toxicity.

Pazopanib tablets: For step-wise dose reductions, see Appendix II for the dosing nomogram.

Pazopanib powder in suspension: For step-wise dose reductions see Tables 1 and 1a (Section 4.1.1).

5.2.1 For all patients:

If Grade 4 neutropenia occurs,

- a) Pazopanib should be held.
- b) CBCs should be checked at least twice a week (every 3 to 4 days) until ANC $\geq 750/\mu L$.
- c) Subsequent doses of pazopanib should be given at a reduced dose, when $ANC \ge 750/\mu L$.

If Grade 4 thrombocytopenia occurs,

- a) Pazopanib should be held.
- b) CBCs should be checked at least twice a week (every 3 to 4 days) until platelet count \geq 75,000/µL without need for platelet transfusion in the preceding 7 days.

Subsequent doses of pazopanib should be given at a reduced dose, when platelet count \geq 75,000/µL without need for platelet transfusion in the preceding 7 days.

- 5.2.1.1 If dose-limiting myelosuppression occurs as noted in Section 5.1.1,
 - a) The dose of pazopanib should be resumed at a reduced dose, once ANC $\geq 750/\mu L$ and platelet count $\geq 75,000/\mu L$ without need for platelet transfusion in the preceding 7 days.
- 5.2.2 For patients who have a dose limiting hematological toxicity that does not resolve to the parameters defined in Section 5.2.1 within 14 days of holding pazopanib: if re-challenge is to be considered the Study Chair must be contacted and provide approval prior to re-challenge.

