5.3 Dose Modifications for Non-Hematological Toxicity

Specific instructions for the management of potential pazopanib side effects are included in Section 5.4.

- 5.3.1 For any non-hematologic dose limiting toxicity as detailed in Section 5.1.2:
 - a) Pazopanib should be held
 - b) If the non-hematologic DLT is a pazopanib specific toxicity, the dosing guidelines in Section 5.4 should be followed
 - c) If the non-hematologic DLT returns to baseline within 14 days of holding pazopanib, subsequent doses of pazopanib should be given at a reduced dose.
 - If toxicity does not resolve to meet continued treatment parameters within 14 days of drug discontinuation, and if re-challenge is to be considered, the Study Chair must be contacted as outlined in Section 4.2 to discuss.
 - If DLT recurs in a patient who has resumed treatment after the maximum allowed dose reductions, the patient must be removed from protocol therapy, unless the patient has been approved for a further dose reduction following discussion with the Study Chair.

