- If BP is > 25 mm Hg above the ULN hold pazopanib, monitor BP, and administer/adjust anti-hypertensive therapy as clinically indicated.
 - \circ If the BP returns to \leq ULN within 14 days, pazopanib may be restarted at a reduced dose.
 - If the BP is > ULN for >14 days, the patient must be removed from protocol therapy (Section 8.1).

Arm 5 of algorithm:

If the participant develops Grade 4 hypertension, **discontinue** pazopanib, monitor BP and administer anti-hypertensive therapy as clinically indicated. A nephrology and/or cardiology consult is recommended. The patient must be removed from Protocol Therapy (Section 8.1).

5.4.2 Abdominal pain:

Abdominal pain is a common symptom with vascular endothelial growth factor (VEGF) receptor antagonists such as pazopanib. Bowel perforations have been reported in clinical trials of pazopanib and with other agents in this class. Bowel perforations have been associated in some patients with tumor in the bowel wall, or diverticulitis, while in others there has been no clear explanation.

Although bowel perforation is a rare event, investigators and study staff at the site are advised to be vigilant of this potential complication in patients receiving pazopanib. Abdominal complaints should be assessed during AE review at every visit. In addition, every physical exam should include a complete abdominal exam. For patients with abdominal complaints and/or abnormal findings on clinical exam, follow the dose modifications and evaluations described below.

Adverse events & descriptions	Dose Modifications & Evaluations
Mild to Moderate abdominal pain or other abdominal complaints with no associated abnormal findings on physical exam	 Continue pazopanib at current dose Implement supportive care as indicated and per institutional standards; consider imaging studies Advise the patient to seek medical attention should their complaints worsen Appropriate follow-up until complaints resolve or origin of the pain is identified. Imaging studies to confirm the absence of abdominal pathology should be performed based on the investigator judgment.
Severe abdominal pain or a concerning abdominal exam	 Hold pazopanib Recommend obtaining appropriate imaging studies to evaluate the patient's specific complaints or exam findings Resume pazopanib at previous dose if imaging studies confirm the absence of abdominal pathology
Confirmed diagnosis of abdominal perforation	1. Remove from protocol therapy

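### The SAP specifies toxicity, exposure and DLT summaries by tumour cohort only, so none separates the tablet from the above-MTD suspension dose that protocol 9.8.2.6 had in view (minor)

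*Protocol*

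**What the plan says.** **Safety display**

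- Protocol 9.8.2.6 presents safety for the whole safety population, whatever the tumour cohort. If the suspension was given at more than one dose level, each level gets a separate column.
- Protocol 9.7.3 asks that departures from the protocol's analysis plan, and additions to it, be recorded in the RAP (the SAP here) and in the final study report.
- SAP 11 reports safety by cohort, SAP 11.1 summarises exposure and dose received by cohort, and SAP 11.2 counts patients with DLTs in each cohort. SAP 8.3 requires no safety subgroups.
- SAP 12.3.1 and 12.4 split PK parameters and steady-state troughs by dose and formulation.

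**Suspension dose review**

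- Protocol 4.1 starts the suspension at 225 mg/m², above the Phase I MTD of 160, and states that "Safety and PK data from these patients will be reviewed prior to further enrollment of patients requiring powder suspension".
- Protocol 2.5 says "Six evaluable patients are required". Two or more patients with DLTs among those six halt enrolment at 225, and new suspension patients then start at 160.
- A patient is evaluable after at least 24 days at 225 in Cycle 1, or if "withdrawn from dosing due to one or more protocol-defined dose-limiting toxicities" during that cycle. Neither document defines the phrase.

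**The concern.** Tolerability of the suspension at 225 mg/m² is one of the few safety questions specific to this trial, because the dose was deliberately set above the Phase I MTD. Further characterisation of toxicity (aim 1.2.2) and of suspension PK (aim 1.2.3) are both secondary aims. Under the SAP text a reader could see exposure to the suspension by dose, but could not see its toxicity in any specified summary.

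Tumour cohort is not a stand-in for formulation. Tablets require a BSA of at least 0.84 m² (protocol 3.2.4), so the smallest children can only receive suspension. The share on suspension is therefore likely to differ between tumour cohorts, in proportions the documents do not give.

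The undefined evaluability phrase adds a second, smaller reason for the same table. Only evaluable patients enter the 2-of-6 count. If a patient with a DLT that was held and restarted at 160 was treated as non-evaluable, the formal count alone would not show it.

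**Working it through.** **1. Meaning of cohort.** SAP 2 defines each cohort by tumour type. SAP 12.3 once uses the word for the suspension group, but SAP 11 gives no sign of that meaning.

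**2. The two documents side by side.**

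| Item | Protocol | SAP |
|---|---|---|
| Safety tables | 9.8.2.6: all patients together | 11: by tumour cohort |
| Suspension dose level | 9.8.2.6: separate columns if more than one | 11 to 11.2: not mentioned |
| Formulation, toxicity | not asked for | 11 to 11.2: not mentioned; 8.3: no safety subgroups |
| Dose and formulation, PK | 9.11: separated if needed | 12.3.1, 12.4: separated |
| Record of a change | 9.7.3: required | none found |

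**3. What mixing does to the exposure table.** Target doses differ by 450/225 = 2, and daily caps by 800/400 = 2. At a BSA of 1.0 m² the tablet nomogram gives 400 mg and the suspension 225 mg. SAP 11.1 averages daily dose in mg within tumour cohort, so that mean depends on the formulation mix as well as on dose reductions.

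**4. The evaluability threshold.** The plan's own figure reproduces: 24/28 = 85.7%, against the stated 85%.

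**5. Who could fall between the two limbs.** On the Cycle 1 map, blood pressure, CBC, ALT, amylase and lipase are checked on Days 8, 15 and 22. A DLT found then follows at most 8, 15 or 22 days at 225, all below 24. Usual handling is a hold and then a lower dose:

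- Grade 4 cytopenia, after recovery: "Subsequent doses of pazopanib should be given at a reduced dose" (5.2).
- Other non-hematologic DLTs: "If the non-hematologic DLT returns to baseline within 14 days of holding pazopanib, subsequent doses of pazopanib should be given at a reduced dose" (5.3.1).
- Hypertension, after control within 14 days: "pazopanib may be restarted at a reduced dose" (5.4.1).

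The first suspension reduction is to 160 (Table 1 in 4.1.1). If withdrawal means permanent stopping, such a patient meets neither limb.

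The route is narrow:

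- Hold, recovery and restart arguably must all fall within 28 days, since a patient still off drug at the end of Cycle 1 arguably was withdrawn during it.
- Grade 3 ALT, the DLT reported at suspension 225 in Phase I (2.4.1), restarts only with recovery in 14 days, evidence of benefit, approval and re-consent (5.4.3). Yet "Tumor response will be evaluated using appropriate imaging assessments at baseline, prior to Cycle 3", so no response scan is scheduled after baseline until the end of Cycle 2.
- Scheduled urinalysis falls on Day 1 and then in the Day 25-28 window, so proteinuria found on schedule would normally follow 24 days of dosing.
- DLTs that end treatment count on either reading.

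**6. Conditional effect of one omission.** The documents give no operating characteristics for the 2-of-6 rule. Let X ~ Binomial(6, p) be the DLTs in the first six, with p assumed. If one DLT patient is left out and replaced once, the verdict changes only when X = 2 and the replacement has no DLT:

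P(change) = P(X = 2) × (1 − p)

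| Assumed p | P(X = 2) | P(change) | P(halt), none omitted | P(halt), one omitted |
|---|---|---|---|---|
| 0.20 | 0.246 | 0.197 | 0.345 | 0.148 |
| 1/3 | 0.329 | 0.219 | 0.649 | 0.429 |
| 0.40 | 0.311 | 0.187 | 0.767 | 0.580 |
| 0.50 | 0.234 | 0.117 | 0.891 | 0.773 |

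The last column is the fourth minus the third. It supposes that an omission occurs whenever there is a DLT to omit. With no omission the change is zero.

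**7. Precision.** Exact (Clopper-Pearson) 90% intervals are 1% to 58% for 1 of 6 and 6% to 73% for 2 of 6.

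**The case against.** Several points on the other side stand.

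- **An all-patient total may exist.** SAP 11.2, 11.4 and 11.5 sort AE tables by total incidence, which implies one. A reader might infer that toxicity appears only within tumour cohorts; the text does not show that. A total would still mix the two formulations.
- **The dose-column rule is conditional.** The documents do not say whether 160 was ever a starting dose. A reader might infer that the SAP dropped a binding column requirement; if only 225 was used, that sentence called for nothing. The protocol's display across all cohorts, by contrast, carries no condition.
- **The protocol never asks for tablet against suspension.** That split is an addition.
- **Detail is available elsewhere.** DLT and by-subject exposure listings are planned, SAP 11 does not claim to be exhaustive, and the table shells are a separate document not seen here. Listings, however, are not summaries.
- **A hold can reasonably count as withdrawal.** Protocol 5.1.1 defines one DLT as "Any hematologic toxicity requiring dose reduction or treatment interruption for >14 days", 5.3.1 refers to a hold as discontinuation of drug, and permanent stopping has its own wording elsewhere. On that reading every held DLT patient is evaluable. The opposite reading has support too: SAP 11.5 lists treatment withdrawal apart from dose interruptions. The text does not settle it.
- **The review was not only a count.** SAP 4.1 has the team look at the whole safety and tolerability profile of the first suspension patients.

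None of these supplies a specified toxicity summary by formulation or suspension dose.

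**Conclusion.** The display point holds. The SAP's safety sections neither carry over protocol 9.8.2.6 nor record the change as 9.7.3 asks, and as specified they leave tablet 450 and suspension 225 mixed in every toxicity summary while PK is separated. This rests on the SAP text alone.

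Severity is minor. SAP 4.3 records that the study was declared futile, so no dosing decision can change, and the primary endpoint is untouched.

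The evaluability wording is an unresolved ambiguity, not a demonstrated fault. A reader might infer from the table in step 6 that 225 mg/m² was wrongly passed as tolerated. The documents do not support that: they record no omitted patient, give no DLT rate in this trial, and allow a reading under which no omission is possible. The probabilities show only how sensitive a 2-of-6 rule is to one patient, which is reason enough to state how such patients were counted.

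**What to change.** Add to SAP 11, 11.1 and 11.2 exposure, AE and DLT tables pooled over tumour cohorts, with columns by formulation and by each suspension starting dose actually used. If only 225 was used, that is one tablet and one suspension column. The dose-level columns restore the protocol's conditional rule; label the formulation split as an addition. If the SAP is already closed, the RAP addendum and study report route in SAP 8 serves.

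In the DLT table, give Cycle 1 DLTs as counts among all suspension patients at each starting dose. Include any patient with a Section 5.1 DLT, whether the drug was held, reduced or stopped. Add a note saying whether any such patient was treated as non-evaluable in the 2-of-6 review; if none was, the question is closed. The protocol need not be amended.

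The cost is a few tables from data already collected, using variables the PK analysis needs anyway. It requires no new patients and no change to the threshold. The suspension dose may look less favourable, and the counts will be small, so they should not be presented as a comparison of rates.
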